## **A. Introduction**

Poverty has been identified as a powerful predictor of child maltreatment and child welfare involvement. Recent research shows that even modest economic and concrete supports are associated with reduced child maltreatment and involvement with child welfare. Toward that end, the New York State Office of Children and Family Services (OCFS), in partnership with the Office of Temporary Disability Assistance (OTDA) and the Center for Guaranteed Income Research (CGIR), University of Pennsylvania is conducting a randomized controlled trial of unconditional cash transfers among families with prior child welfare referrals in three New York counties in 2023.

## **B. Treatment**

The project will enroll approximately 150 households in Monroe, Onondaga, and Westchester counties in New York state to receive \$500 per month, unconditionally, via a debit card over a one-year period, totaling \$6,000 per family. Another 300 will be assigned to the control group and will not receive the unconditional cash transfers but will be eligible to participate in research activities. Families will be eligible if they have a recently closed case managed by OCFS through their differential response system, called Family Assessment Response (FAR) in New York State. FAR is used for CPS reports that have been accepted by the New York State Central Register for Child Abuse and Maltreatment (SCR) where there is no safety concern that rises to the level of immediate or impending danger for the child and/or family. Often, families served in the FAR track have been referred for poverty-related social needs.

## **C. Randomization and Participant Eligibility**

Households referred and determined eligible for Family Assessment Response (FAR) will be invited to participate in a randomized controlled trial of unconditional cash transfers. Approximately 150 individuals will be randomly assigned to the treatment group and will receive monthly \$500 unconditional cash transfers for one year. Another 300 will be assigned to the control group and will not receive unconditional cash transfers but will be eligible to participate in compensated research activities. We will randomly select 50 individuals per county into the treatment arm, and 100 individuals per county into the control arm.

Youth Research Inc. (YRI), an agency contracted by the New York Office of Child and Family Services (OCFS), will disburse treatment funds on a debit card. Longitudinal repeated measures will be collected through online surveys conducted before treatment begins, at 6 months after treatment begins, 12 months after treatment begins, and 18 months (6 months after treatment ends). Future maltreatment reports and case outcomes handled by OCFS will be measured using agency administrative data.

### **Eligibility Criteria:**

To participate in this pilot, caregivers must meet the following eligibility criteria:

- Received an invitation from an OCFS caseworker to apply
- Have met the state eligibility requirements for the Family Assessment Response (FAR) program within the previous six months
- Live in Monroe, Onondaga, or Westchester County, New York
- Be 18 years of age or older at the time of application.

## **D. Data, Study Sample, Outcomes, and Other Variables**

### **D.1. Data and Study Samples**

The study sample will be recruited from the population of eligible households in Monroe, Onondaga, and Westchester counties, New York. We will randomly select 50 households per county into the treatment arm, and 100 households per county into the control arm.

Data will be obtained from two sources:

1) A web-based survey for all study participants at baseline, at 6 months after treatment begins, at 12 months after treatment begins, and at 18 months after treatment begins (6 months after treatment ends). This survey will collect information on caretaker and child demographic, health, behavioral, educational, and social characteristics. All variables will be collected at baseline. We will repeat data collection for all time-varying variables at each post-baseline wave of the survey.

2) OCFS administrative records linked to the study participants and their children using the DOB and name of the study participant and all minor children in the participant's household. Data will be provided by OCFS as family-specific and child-specific counts of a series of events related to child maltreatment reports and agency interventions.

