### **D.2. Planned Outcomes**

#### **Primary Outcomes:**

Primary outcomes are measured as event counts between baseline and 18 months after the beginning of study interventions using OCFS administrative data. We will treat all primary outcome events as integer count variables, with the exception of preventive services which will be treated as binary (services delivered / no services delivered). In the event that observed study outcomes are rare in the sample, we will treat primary outcomes as binary (occurred / did not occur) instead of treating rare outcomes as event counts.

The primary study outcomes (and variable class) are:

- Investigative Track OCFS maltreatment cases: event count
- Family Assessment Response (FAR) track OCFS cases: event count
- Total OCFS cases: event count as sum of investigative track and FAR track cases
- Indicated OCFS maltreatment investigations: event count
- Substantiated OCFS maltreatment investigations: event count
- OCFS foster care placements: event count
- Preventive services for families at risk of foster care: binary

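### All seven primary outcomes rest on a name-and-birth-date link with no indicator that it succeeded, although each family's qualifying FAR case could confirm it cheaply

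*Combined protocol and SAP*

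**What the plan says.** Section D.1 gives one linkage key for the administrative data: "OCFS administrative records linked to the study participants and their children using the DOB and name of the study participant", together with those of the household's minor children. On what comes back, it says "Data will be provided by OCFS as family-specific and child-specific counts of a series of events". It names no case number or person identifier, match indicator, match-rate report or procedure for families that cannot be found.

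Section D.2 puts every primary outcome on this source: "Primary outcomes are measured as event counts between baseline and 18 months after the beginning of study interventions using OCFS administrative data". Six of the seven are counts and one, preventive services, is binary. If events prove rare, "we will treat primary outcomes as binary (occurred / did not occur) instead of treating rare outcomes as event counts". Neither form has a category for a family that was not linked.

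Other sections show that each family comes from an OCFS case. Section B states: "Families will be eligible if they have a recently closed case managed by OCFS through their differential response system". The eligibility criteria in section C require an invitation from an OCFS caseworker and that the caregiver "Have met the state eligibility requirements for the Family Assessment Response (FAR) program within the previous six months". Section E.2 takes the county effect from the OCFS case that qualified the family.

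Two provisions come near the gap. The multiple-imputation rule in D.3 covers covariates. E.1 plans attrition and balance checks but does not mention linkage failure.

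**The concern.** Links on name and birth date can fail through spelling variants, name changes or wrong dates. In a survey a lost participant shows up as missing. In an extract of event counts a participant who was not found may show up as having no events, which is the favourable outcome here. The counts themselves cannot expose this. They start at baseline, and the qualifying case, closed before enrolment, will normally precede that date, so a correctly linked family may also have nothing in the window.

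At stake is the whole primary outcome set. Undetected missed links would understate event frequency in the sample and the absolute treatment effect. If the arms were missed at different rates, the intent-to-treat comparison would be biased.

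**Working it through.** **No stated figure to reproduce.** The documents give no event rate, effect size, power or match rate. The only arithmetic is the allocation, and it agrees: 3 counties × 50 = 150 treated and 3 × 100 = 300 controls, 450 families in all. Every risk and match rate below is an assumption chosen to show scale.

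**Step 1. Is a non-match visible?** Setting the sections side by side:
- D.1: the key is name and birth date; the return is counts; no indicator.
- D.2: the outcome is a count or an occurred/not occurred variable; no unlinked state.
- D.3: imputation for covariates only.
- E.1: attrition checks, which would pick up unlinked families only if they arrive as missing.

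The plan therefore does not ensure that a non-match can be told from a true zero.

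**Step 2. Equal failure in both arms, if non-matches are read as zero.** Let m be the share of families missed, and p0 and p1 the true control and treated risks.
- Observed risks: p0(1 − m) and p1(1 − m).
- Observed ratio: p1/p0, unchanged.
- Observed difference, the scale on which E.2 defines the average treatment effect: (p1 − p0)(1 − m).

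Power uses the two-sided 5% level in E.5 and the usual normal approximation: Φ[(|d| − 1.96·SE0)/SE1], with SE0 from the pooled risk and SE1 from the separate risks. Assume p0 = 0.30 and a true ratio of 0.6, so p1 = 0.18.
- m = 0: d = −0.120, SE0 = 0.0439, SE1 = 0.0410, Φ(0.829) = 79.7%.
- m = 10%: risks 0.270 and 0.162, d = −0.108, SE0 = 0.0423, SE1 = 0.0395, Φ(0.633) = 73.7%.

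| Missed in both arms | Families of 450 | Difference | Power, p0 = 30% | Power, p0 = 20% |
|---|---|---|---|---|
| 0% | 0 | −0.120 | 79.7% | 56.6% |
| 5% | about 23 | −0.114 | 76.8% | 53.8% |
| 10% | 45 | −0.108 | 73.7% | 51.0% |
| 20% | 90 | −0.096 | 66.8% | 45.4% |

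The difference column is for p0 = 30%; the ratio is 0.6 throughout. An odds ratio from the logistic model for binary outcomes would move slightly: from (0.18/0.82)/(0.30/0.70) = 0.512 to (0.162/0.838)/(0.27/0.73) = 0.523 at m = 10%.

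**Step 3. Unequal failure, again if read as zero.** Observed ratio = true ratio × (1 − mT)/(1 − mC), where mT and mC are the shares missed in the treated and control arms. Both directions are shown because the documents support neither.
- 2% missed in treatment, 10% in control: factor 0.98/0.90 = 1.09. A true 0.70 is seen as 0.76. With no true effect, a nominal 5% test rejects 7.2% to 10.3% of the time for control risks of 20% to 40%.
- 10% missed in treatment, 2% in control: factor 0.90/0.98 = 0.92. A true 0.70 is seen as 0.64, and the test rejects 6.7% to 10.0% of the time.

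**Step 4. What treating non-matches as missing recovers.** With 10% missing in each arm, unrelated to outcome, 270 controls and 135 treated remain. The expected difference returns to −0.120. SE0 = 0.0462, SE1 = 0.0433, and power is Φ(0.679) = 75.1%. The flag alone restores the estimate; most of the lost power returns only if families are re-linked.

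**The case against.** The strongest reply is that this builds on silence. Three stronger readings are tempting, and the documents support none of them.

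- **Non-matches are coded as zero.** D.1 says that data arrive as counts, not that counts are all that arrives. OCFS could return no row, a blank or a flag. If unlinked families came back as missing, the E.1 checks would see them. This stands; what remains is that the plan neither asks for such a signal nor says what to do with it.
- **Matching is worse among controls, because treated families must be identified for a debit card.** D.1 applies one rule to everyone, and nothing ties card issue to the identifiers sent to OCFS. Controls also take part in compensated research activities, so they too are known to the study. The arm-difference figures in Step 3 are illustrations only.
- **An exact identifier was available and ignored.** No section names one. Meeting FAR requirements is not itself a record; that a case exists rests on sections B and E.2. A closed case's number also need not lead to a later case, so OCFS would have to follow the people on it.

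The search also uses the caregiver and every minor child, so a complete miss requires all of them to fail. The all-or-nothing formulas ignore this and probably overstate complete misses. A partial miss, with one child not found, would still undercount without notice.

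**Conclusion.** The point holds as a cheap improvement to the linkage method, not as a demonstrated bias. All seven primary outcomes depend on a link whose failure the plan has no stated way to detect, and each family's qualifying FAR case offers a positive control.

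No size can be derived from the documents. If non-matches were read as zeros equally in both arms, the absolute effect would fall by the share missed. Under the assumed 30% control risk and ratio of 0.6, a 10% miss would cost about 6 percentage points of power (79.7% to 73.7%). Bias in the ratio needs failure that differs by arm, on which the documents give no evidence either way. A reader should not infer that the intent-to-treat comparison is biased; only that the plan could not show that it is not.

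**What to change.** Amend D.1 as follows.

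1. OCFS links through the qualifying FAR case and whatever person records it holds for the people on it, with name and birth date as back-up. The research team need not hold those identifiers.
2. OCFS returns, for each family, a flag that the qualifying FAR case was found.
3. A zero count is accepted only when the flag is positive. Otherwise the family is re-linked and, failing that, its outcome is treated as missing. Because the D.3 imputation rule covers covariates only, add a sentence on how missing primary outcomes are handled.
4. Match rates are reported by arm beside the E.1 attrition checks.

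The cost is one flag in the extract, a small amount of OCFS work and possibly a few families moved from zero to missing. No new participants or study procedures are needed. One limit remains: a family-level flag confirms that the qualifying case was found, not that every child in the household was, so children outside that case still depend on name and birth date.

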### D.3. Participant Characteristics

We will collect the following demographic and socioeconomic information from participants:

- Age
- Gender
- Self-reported race
- Self-reported ethnicity
- Number of adults in household
- Number of children in household
- Educational attainment
- Monthly income from employment
- Monthly income from other government benefits
- Employment
- Health Insurance Status (Insured versus uninsured)
- Child Health Insurance Status (If any child in home is uninsured)
- Housing status

In the event that there are high levels of missingness for any key covariate (i.e., >2%), multiple imputation methods will be used.

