## **E. Statistical Analysis**

### **E.1. Evaluation of randomization, balance, and attrition**

We will test for balance between treatment and control based upon observable baseline characteristics for the overall study population.

Because differential attrition correlated with treatment could introduce bias into our results, we will also evaluate the attrition rate and assess for balance between treatment and control based upon both baseline characteristics for the final analytic sample (and attriters) and potential causes of attrition.

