### **E.2. Statistical specification**

Our primary analytic approach is an analysis based on the intent-to-treat principle that compares outcomes for those randomized into the treatment group to those who were randomized into the control group.

Our models account for time-stable heterogeneity across individuals and treatment sites using random intercepts for each individual enrolled in the study, for each time period during which surveys are collected, and for the county from which their qualifying OCFS case originated. These random effects adjust for correlation induced by repeated measurements of individuals over time, time period effects, and clustering of outcomes within counties.

Our regression models for outcome variable  $y$  take the following general form:

$$\mu = E(y|T, X) = \alpha_i + \delta_j + \gamma_k + \beta T_i + c_j T_i + \theta X_{ij}$$

$$\begin{pmatrix} \alpha \\ \delta \\ \gamma \end{pmatrix} \sim N(0, \Sigma)$$

Where  $T$  indicates selection into the treatment group,  $X$  is a matrix of demographic characteristics,  $i$  indicates an individual participant,  $k$  indicates county of residence at the time of study enrollment,  $j$  indicates survey time period,  $\alpha$  is a vector of individual-level intercepts,  $\delta$  is a vector of time period intercepts,  $\gamma$  is a vector of county-level intercepts,  $\beta$  is the time-stable component of the treatment effect,  $c$  is a vector of time-varying components of the treatment effect, and  $\theta$  is a vector of coefficients for demographic predictors.

The relationship between the treatment and outcomes of interest may vary as a function of time. We treat temporal relationships as potentially nonlinear, and model the relationship between time, treatment, and outcomes of interest using a series of time-period intercepts. We estimate a unique intercept for each treatment period as well as an interaction between treatment status and treatment period to capture time-varying effects of treatment.

For all continuous (additive index) outcomes with a roughly symmetric distribution, we treat the outcome as following a linear model where

$$y \sim N(\mu, \sigma^2)$$

For all binary outcomes, we treat the outcome as following a Bernoulli model

$$y \sim \text{Bernoulli}(p)$$

$$E(p|T, X) = \text{logit}^{-1}(\mu)$$

And for all count outcomes and additive index outcome with a non-symmetric distribution, we treat the outcome as following a negative binomial model

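### The plan does not provide for pre-baseline OCFS counts, either for the balance check or as a covariate for the primary outcomes

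*Combined protocol and SAP*

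**What the plan says.** - **Agency data.** D.1 describes the second data source: "Data will be provided by OCFS as family-specific and child-specific counts of a series of events related to child maltreatment reports and agency interventions". Linkage uses the names and dates of birth of the participant and the household's minor children. No period is given for the extract.
- **Purpose.** The only use of these records that section C states is forward-looking: "Future maltreatment reports and case outcomes handled by OCFS will be measured using agency administrative data".
- **Primary outcomes.** D.2 defines them as "event counts between baseline and 18 months after the beginning of study interventions".
- **Baseline collection.** D.1 also says "All variables will be collected at baseline", but this sentence belongs to the web survey, not to the agency records. D.2 lists a baseline wave for the secondary outcomes.
- **Characteristics.** D.3 opens with "We will collect the following demographic and socioeconomic information from participants" and lists 13 items. None is a prior report, case, placement or service.
- **Balance.** E.1 says "We will test for balance between treatment and control based upon observable baseline characteristics for the overall study population" and does not list the variables.
- **Covariates.** In E.2, X "is a matrix of demographic characteristics".

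**The concern.** The survey outcomes have a pre-treatment measurement; the seven primary outcomes do not. Past agency contact is the baseline variable most directly related to future agency contact. Every enrolled family met the FAR requirements within the previous six months, so each has some recent history with the agency whose records are to be linked.

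As written, a balance table could show good agreement on age, income and household size and be silent on prior reports. The primary models would also forgo whatever precision that history offers. This matters more than usual here: there are 150 treated families, D.2 itself foresees rare events, several primary outcomes share a multiplicity adjustment, and no power calculation is given.

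**Working it through.** The plan states no power, event rate or baseline correlation, so it has no figure to reproduce beyond the sample size: 3 × 50 = 150 treatment and 3 × 100 = 300 control families.

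**1. What is provided for.** D.2 fixes the outcome window, D.1 leaves the extract window open, D.3 omits agency history, and E.2 restricts X to demographics. E.1 leaves its list open. Prior history is thus neither requested nor named for any use, and neither is it excluded.

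**2. Chance imbalance.** The SE of a standardised baseline difference is √(1/150 + 1/300) = 0.100. The two-sided probability of a difference larger than d is 2[1 − Φ(d/0.100)]:
- d = 0.10: about 32%
- d = 0.15: about 13%
- d = 0.20: about 4.6%

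In a linear approximation, an imbalance of d SD in a covariate with correlation r to the outcome shifts the unadjusted estimate by r × d. With d = 0.15 and an assumed r of 0.4, that is 0.06 SD, or 0.6 of the 0.100 SE. With r = 0.2 it is 0.03 SD.

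**3. Precision, linear approximation.** The detectable difference at 80% power and two-sided 0.05 is (1.960 + 0.842) × 0.100 = 0.280 SD. Adjustment multiplies it by √(1 − r²), and the equivalent unadjusted total is 450/(1 − r²). The values of r are assumptions.

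| r | Detectable difference (SD) | Power where unadjusted power is 80% | Equivalent total N |
|---|---|---|---|
| 0.1 | 0.279 | 80.4% | 455 |
| 0.2 | 0.274 | 81.6% | 469 |
| 0.3 | 0.267 | 83.6% | 495 |
| 0.4 | 0.257 | 86.4% | 536 |
| 0.5 | 0.243 | 89.9% | 600 |

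**4. Precision, count model.** This is a gamma-Poisson simulation with 150 v 300 families, rate ratio 0.75, a 24-month prior count and a family propensity that does not change. Negative binomial models were fitted with and without log(prior count + 1), with 200 replicates per setting. All rates and shapes are assumptions.

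| Events per control family | Gamma shape | Median SE without | Median SE with | Variance ratio |
|---|---|---|---|---|
| 0.5 | 0.5 | 0.211 | 0.184 | 0.76 |
| 0.5 | 1 | 0.188 | 0.177 | 0.89 |
| 1 | 1 | 0.149 | 0.130 | 0.76 |
| 1 | 2 | 0.132 | 0.124 | 0.89 |

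For example, (0.130/0.149)² = 0.76, a 24% reduction. The table therefore spans 11% to 24%, and repeat runs agreed to within about 2 percentage points.

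**5. Sensitivity of that gain.**
- One qualifying case added to every family's history: about 10% to 25%, essentially unchanged.
- Half the families redraw their propensity: about 2% to 7%.
- Propensity correlated 0.5 between periods: 2% to 4%.
- Stable propensity but only 0.1 to 0.2 events per family: about 1% to 3%.
- Logistic models: no reduction in the SE of the log odds ratio in any setting, which is expected because the adjusted odds ratio is a different quantity. The median z rose by at most about 0.17.

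Selection of families on a recent event was not simulated.

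**The case against.** The strongest reply is that randomisation within county already makes the comparison valid. Chance imbalance in an unadjusted prognostic factor is part of what the standard error measures. That stands: a reader might infer that the primary estimate is biased without this history, and it is not.

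A reader might also infer that OCFS data are drawn only from baseline onward. The documents do not say so. The baseline-to-18-month window defines the outcomes, and the forward-looking sentence in section C describes what will be measured; D.1 puts no dates on the extract. Nor do they support saying that history is unavailable or that nothing could reveal an imbalance. The records come from the same linked source, and the open wording of E.1 could take in agency history. What the text supports is that this history is not planned or specified. The open wording helps only so far, because no listed variable supplies it and a covariate chosen after outcomes are seen would be open to challenge.

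The third reply is that the gain may be negligible. That stands as a possibility. The upper figures need stable family propensity and at least 0.5 events per family. Preventive services is always binary, and D.2 allows rare outcomes to become binary, where the variance figure does not apply. The qualifying contact is common to all families, so the useful variation lies in earlier history.

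**Conclusion.** The point holds as a gap in specification and a cheap improvement, not as a threat to validity. Pre-baseline OCFS counts are not requested, not named for the balance check and not among the model covariates. The cost is a missing check on the characteristic closest to the primary outcomes, plus some lost precision: roughly 1% to 24% of the variance of the log rate ratio, for count models only. Where in that range the trial falls depends on event rates and on the persistence of family propensity, neither of which the documents give. The imbalance probabilities in step 2 need neither; they rest only on the 150 v 300 allocation and a normal approximation.

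**What to change.** - **D.1:** state the period the extract covers, and request the same OCFS counts for a fixed look-back ending at randomisation (for example 24 months) for every linked family in both arms.
- **E.1:** name these counts in the balance table.
- **E.2:** prespecify one prior-history covariate for the primary-outcome models, for example the log of prior total cases + 1, with the qualifying case counted the same way for all families. Fix it before outcomes are seen. For outcomes analysed as binary, note that the odds ratio is then conditional on this covariate.

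The cost is a few more columns in an extract already planned, with no participant burden. It depends on consent and the data agreement covering the look-back, which cannot be judged from the text available. Families that recently moved into the state will have incomplete history. Randomisation makes this equally likely in both arms, so it weakens the covariate without biasing the comparison.
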